In Phase 1, we will develop the MAP to Health online web-based interview that will be used to explore what is particularly meaningful to participants, how PA is consistent with those goals, and what activities patients plan to engage in. Participants (N=12) will complete the interview and rate the ease of use, usefulness, intention to use, and theoretical fidelity of the intervention.

In Phase 2, we will conduct a proof-of-concept pilot trial using a double-pretest single group design. Participants (N=35) will complete a 4-week pretest monitoring period and an 8-week pilot trial of the intervention, with assessments of SDT mechanisms and meaning salience at pretest (-4 weeks), baseline (0 weeks), midpoint (4 weeks) and posttest (8 weeks). In addition, participants will wear accelerometers to assess PA during the 12 weeks.

2. Study Aims

Aim 1 (Development): To assess the acceptability of underlying theoretical and technological frameworks of the web-based MAP to Health interview.

H1a: Participants will rate the web-based interview as easy to use and useful and will report intentions to use the intervention.

H1b: The web-based interview will solicit data necessary to program theory-based, personalized text messages for participants.

Aim 2 (Proof-of-concept testing): To determine whether MAP to Health is related to changes in theoretically identified behavior change mechanisms.

H2: Participants will experience increases in the theoretically identified mechanisms of behavior change (i.e., meaning salience, internal motivation, and basic needs satisfaction) after receiving the MAP to Health intervention compared to a pre-test no intervention period.

Exploratory Aim: To assess whether the intervention and increases in the hypothesized behavior change mechanisms (meaning salience, internal motivation, and basic needs satisfaction) are associated with increases in PA compared to the pretest no intervention period.

3. Background, Rationale, Significance

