To identify potential participants, we will use electronic health records (EHRs) of patients from HealthPartners, Park Nicollet, and Stillwater Medical Group clinics who meet eligibility criteria. Then the Programmer Analyst will randomly select potential participants to recruit and screen. Recruitment samples will be stratified on sex and race/ethnicity; specifically, we will oversample racial and ethnic minorities to ensure adequate representation.

Because some eligibility criteria are not available in EHR, potential participants will be further assessed for eligibility during the phone screening process. Estimating a 2-3% participation rate, we will pull a recruitment sample of 2250 patients: 250 in Phase 1 and 2,000 in Phase 2.

For Phase 1, we will recruit up to 20 participants for usability testing. We anticipate that we will recruit a minimum of 12 participants, with three rounds of 4 participants. This sample size was chosen because it is the industry standard for this type of usability testing (~10 participants). We have included an additional 8 participants in case we need to conduct additional rounds of usability testing.

For Phase 2, we will recruit up to 45 participants for the proof-of-concept pilot trial. Our power analysis indicates that a minimum of 35 participants is needed to detect a meaningful change in the hypothesized mediators (see Phase 1 Power Analysis for details).

c. Data collection process

i. Identifying Participants

Potential participants will be identified EHRs by a Research Informatics Programmer Analyst. The Programmer Analyst will use available inclusion/exclusion criteria above to identify potentially eligible patients, stratify on sex and race/ethnicity, apply a random selection algorithm to that list, and check the research opt-out list. Once the list of potentially eligible participants has been narrowed to the appropriate sample size, the analyst will then pull demographics and contact information.

For Phase 1, we may also offer the study to employees of HealthPartners who believe they meet the study inclusion exclusion/criteria.

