2. Meaning Salience. Meaning salience is a primary outcome for Aim 2. The Meaning Awareness Scale (MAS) is a 6-item measure that assesses meaning salience.⁶³ Participants rate the extent to which they were aware of meaning over the past day (e.g., “I was aware of the meaning in my life” on a 7-point Likert type scale ranging from 1 (*rarely*) to 7 (*very often*)). Items are summed for a total score. Participants will complete the MAS on three random days during each of the four assessment periods and total scores will be averaged across those three days.
3. Basic Psychological Needs Satisfaction. Basic needs satisfaction is a primary outcome for Aim 2. The Psychological Needs Satisfaction in Exercise Scale (PNSE)⁶⁴ will be used to measure satisfaction of needs of autonomy (e.g., “I feel free to exercise in my own way”), competence (e.g., “I feel confident in my ability to perform exercises that personally challenge me”), and relatedness (e.g., “I feel attached to my exercise companions because they accept me for who I am”) in exercise contexts. The PNSE has 18-items that participants rate on a 6-point Likert-type scale ranging from 1 (false) to 6 (true). Items are averaged within and across the subscales for total scores. Previous research has demonstrated that the PNES has strong internal consistency reliability ($\alpha \geq .90$), construct validity, and convergent validity.⁶⁴
4. Internal Motivation. Internal motivation is a primary outcome for Aim 2. Motivation internalization will be measured using the Behavioral Regulations in Exercise Questionnaire, version 4 (BREQ-4).⁶⁵⁻⁶⁷ The 28-item BREQ-4 assesses motivations for exercise on the SDT continuum. There are 7 subscales with 4 items each: amotivation (e.g., “I don’t see why I should have to exercise.”); external regulation (e.g., “I exercise because other people say I should.”); introjected regulation-avoidance (e.g., “I feel guilty when I don’t exercise.”); introjected regulation – approach (e.g., “I

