Aim 2 Power. In this pilot, the aim is not to determine statistical significance but rather to assess whether MAP to Health is likely to increase the hypothesized mediators enough to elicit meaningful change in PA (Cohen's $d \geq 0.30$). Based on our previous observational study,⁵² the strength of the observed relationships in Figure 1 are expected to be $\beta = .55$ (needs satisfaction to internal motivation), $\beta = .30$ (internal motivation to PA), $\beta = .16$ (needs satisfaction to meaning salience), and $\beta = .10$ (meaning salience to PA). Therefore, if half of the total intervention effect ($d = .30/2 = .15$) is mediated through the pathways in Figure 1, then the intervention will need to increase both needs satisfaction (estimated $\beta = .50$) and meaning salience (estimated $\beta = .60$) by $d > 0.55$. The remaining $d \approx 0.15$ of the total effect would be represented as a direct effect on PA and could be obtained at least in part via unmeasured mediators. If the week -4 vs. week 0 comparison yields a difference of approximately 0, the week 4 vs. week 0 comparison is similar in power to a paired t -test. A paired t -test with a sample size of $N = 35$ is powered (0.80, $\alpha = 0.05$) to detect differences of $d \geq 0.49$. As such, the planned analyses may be sufficiently powered to detect meaningful within-person changes in the hypothesized mediators.

h. Strengths and Limitations

This study has several strengths, including building off a previously developed prototype intervention that used a psychometric approach to intervention development (COMAP), using a systematic approach to developing and testing the intervention (using the ORBIT and SOBC models), and building off a solid base of observational and interventional research based on SDT and meaning. Further, we have a strong interdisciplinary team with the resources to carry out the proposed work.

The study is designed as a proof-of-concept pilot trial. Participants will serve as their own controls instead of being compared to a no-intervention control group and our sample size is small. These design choices were made to ensure the intervention was related to changes in the hypothesized

mechanisms; however, we will be limited in our abilities to state that the intervention was related to changes in physical activity.

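### Sections 4.g and 4.b.ii rest N = 35 on all the hypothesized mediators, but no required shift is derived for internal motivation, one of the three primary Aim 2 outcomes

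*Combined protocol and SAP*

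**What the plan says.** Section 4.g (Aim 2 Power) lists four standardized paths from an earlier observational study:

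- needs satisfaction to internal motivation, .55
- internal motivation to PA, .30
- needs satisfaction to meaning salience, .16
- meaning salience to PA, .10

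It supposes that half of a total PA effect of d = 0.30, so 0.15, "is mediated through the pathways in Figure 1". It infers that "the intervention will need to increase both needs satisfaction" (estimated β .50) and meaning salience (estimated β .60) by d > 0.55. It sets this against a paired t-test with N = 35, which has 80% power at α = 0.05 for d ≥ 0.49, and concludes that "the planned analyses may be sufficiently powered to detect meaningful within-person changes in the hypothesized mediators".

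Section 4.b.ii repeats the conclusion without the 'may be': "a minimum of 35 participants is needed to detect a meaningful change in the hypothesized mediators".

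Section 4.e.iv, item 4, states: "Internal motivation is a primary outcome for Aim 2". Hypothesis H2 in section 2 names internal motivation beside meaning salience and needs satisfaction. Section 4.f plans the same time contrasts for each of the three.

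Section 4.g also says that in this pilot "the aim is not to determine statistical significance". The last sentence of the exploratory analysis in section 4.f says much the same and commits to effect sizes.

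**The concern.** The conclusion covers three outcomes, but the derivation covers two. Internal motivation appears in section 4.g only as a link in the chain (.55 in, .30 out). No shift is set as its target, and none is compared with 0.49.

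A shift passed down a path of .55 is roughly half the shift upstream. An upstream shift that just clears 0.49 therefore says little about whether the downstream one does.

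What is at stake is interpretation. Someone relying on section 4.b.ii or the last sentence of section 4.g could take a non-significant internal-motivation contrast as coming from a test with about 80% power, and conclude that this mechanism was not engaged.

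**Working it through.** **Inputs from section 4.g.** N = 35; power 0.80; α = 0.05 (sidedness not stated; two-sided reproduces the figure); the four paths above; mediated effect 0.15; needs-satisfaction value .50; d > 0.55. **From section 4.b.ii.** Recruitment ceiling 45. **Not in the documents.** The pre-post correlation r; 0.3, 0.5 and 0.8 are assumed below.

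**1. The plan's own figure.** For a paired t-test, power comes from the noncentral t with n − 1 degrees of freedom and noncentrality d_z√n. With n = 35 and two-sided 0.05, 80% power is reached at d_z = 0.487, and power at 0.49 is 0.804. The stated 0.49 is reproduced.

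**2. Needs-satisfaction values consistent with the plan.** The plan gives .50 as its estimate and d > 0.55 as the requirement. If needs satisfaction and meaning salience each change by x in total, the mediated effect is x(.55 × .30 + .10) = .265x. Setting this to .15 gives x = .566, which fits d > 0.55. The range is therefore .50 to about .57.

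**3. Implied internal-motivation shift (needs-satisfaction shift × .55).**
- .50 × .55 = .275
- .55 × .55 = .3025
- .566 × .55 = .311

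This is about 0.28 to 0.31.

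**4. Scale.** The path-based d is in units of the outcome's SD, while the paired-t d is in units of the SD of the change. With equal SDs at the two times, d_z = d/√(2(1 − r)), so the two agree only at r = 0.5. The d detectable with 80% power at N = 35 is 0.487 × √(2(1 − r)): 0.58 at r = 0.3, 0.49 at r = 0.5 and 0.31 at r = 0.8.

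**5. Power for internal motivation** (N = 35, complete pairs, two-sided 0.05).

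| Assumed r | d = 0.275 | d = 0.311 |
|---|---|---|
| 0.3 | 0.267 | 0.327 |
| 0.5 | 0.353 | 0.432 |
| 0.8 | 0.705 | 0.807 |

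**6. Correlation needed for 80% power.** r = 1 − (d/0.487)²/2, which gives 0.84 for d = 0.275 and 0.80 for d = 0.311.

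**7. Sensitivity at r = 0.5.** With 45 complete pairs, power is 0.44 to 0.53. With a one-sided test at N = 35, it is 0.48 to 0.56. Using 102 degrees of freedom, as a multilevel model might, the detectable d falls only from 0.487 to 0.478.

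**The case against.** **The claim is already hedged.** Section 4.g says 'may be', both 4.f and 4.g disclaim significance as the aim, and no decision is tied to a test. This stands and keeps the severity low. It does not supply the missing derivation, and section 4.b.ii carries no hedge.

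**The true shift may differ.** This also stands. A reader might infer that .275 is the smallest internal-motivation shift compatible with the plan. It is not. If meaning salience also moves through the .16 path, any pair satisfying .181 × (needs-satisfaction shift) + .10 × (direct meaning-salience shift) = .15 delivers the mediated effect, where .181 = .55 × .30 + .16 × .10. Shifts of .40 and .776 do so, with an internal-motivation shift of .55 × .40 = .22. In the other direction, a direct effect, or the route from meaning to motivation that section 4.d.i describes, would raise the figure. Section 4.g gives no coefficient for either. It places the paths in Figure 1, which is captioned as the study design, while Figure 3 is captioned as the conceptual model. Neither figure is visible in the text available, so the full path structure cannot be checked.

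**The power figure depends on an assumed r.** It does, and r could be high. The one temporal stability the documents report is .82 over two months, for the Satisfaction with Life Scale (section 4.e.iv, item 6). That is a different measure and does not fix r for internal motivation, but at r = 0.82 power would be 75-85%. The plan's direct comparison of 0.55 with 0.49 itself assumes r = 0.5, so that is the fair reference case.

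**The .50 and the d > 0.55.** A reader might also see an error in a needs-satisfaction estimate of .50 beside a requirement of d > 0.55. The plan labels the first as β and the second as d and does not say that they share a scale, so the documents do not establish a contradiction.

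**Conclusion.** The point holds as a gap between what was derived and what was concluded. The sufficiency of N = 35 is argued for needs satisfaction and meaning salience and then stated for a group that includes internal motivation, for which the plan offers no support.

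On the plan's own paths and needs-satisfaction values, an illustrative shift for internal motivation is about 0.28 to 0.31, below the detectable 0.49. At r = 0.5 and 35 complete pairs, power is about 35-43%, so a true shift of that size would be missed roughly 57-65% of the time. Reaching 80% power would need r of about 0.80 to 0.84.

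These figures rest on the listed paths alone, a paired t-test standing in for the multilevel contrast, equal SDs at the two times and an assumed r. They do not show that the trial is too small or that the internal-motivation analysis must fail: r is unknown, the true shift could be larger, and the pilot does not set out to establish significance. Severity is low.

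**What to change.** In section 4.b.ii and in the last sentence of section 4.g, replace 'the hypothesized mediators' with 'needs satisfaction and meaning salience'.

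Add to section 4.g: 'The comparison with d = 0.49 assumes a pre-post correlation of 0.5 and 35 complete pairs. The listed paths imply a shift of about 0.28-0.31 for internal motivation, for which power would be about 35-43% under that assumption, so internal motivation will be interpreted by its effect estimate and 95% CI.'

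The cost is a narrower and less favourable power statement. The reporting sentence applies to one outcome the effect-size emphasis already in section 4.f. Design, sample size and analysis model do not change.

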Appendix A: Phase 1 recruitment materials

MAP to Health Phase 1 recruitment letter v1.0
MAP to Health Phase 1 recruitment email to HPI employees v1.0
MAP to Health Phase 1 phone scripts v1.0
Screening Questionnaire v1.0
Screening Questionnaire_HPI employees v1.0
MAP to Health Phase 1 FAQs v1.0
MAP to Health Phase 1 confirmation and reminder emails v1.0
MAP to Health Phase 1 e-consent v1.0
MAP to Health Phase 1 thank you message

Appendix B: Phase 1 Intervention Tools

Map to Health online assessment v1.0
Map to Health example messages

Appendix C: Survey Measures

Phase 1 Measures v1.0
Phase 2 Measures v1.0

Appendix D: Phase 2 recruitment materials

Phase 2 Activities and Incentives Schedule v1.0
